### Step 3: Test for a mediating relationship of stream segregation for speech recognition in competing speech

We will extrapolate the predictor model for speech recognition in quiet developed in step 2 to the case of speech recognition in competing speech. If the model performs as well for speech in speech as it does for speech in quiet, we would infer that two-talker speech maskers do not introduce meaningful variability into speech recognition outcomes and stop here. If the speech in quiet model is a worse fit, we will add stream segregation to the predictor model and test whether it predicts unique variance in speech recognition accuracy in competing speech. This would demonstrate that stream segregation is a distinct aspect of speech recognition in the presence of competitors. Finally, to complete the mediator analysis we would test whether modulation detection thresholds and memory factors are significant predictors of stream segregation ability.

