## Participants

30 participants who lost their hearing and received cochlear implants as adults will participate in this study. We will include unilaterally and bilaterally implanted individuals listening with their everyday hearing configuration. Individuals with residual acoustic hearing better than 60 dBA at any audiometric frequency will be excluded to avoid the confounding the study with the effects of bimodal hearing. Participants with residual hearing in the non-implanted ear will inset an earplug into that ear to further ensure the stimuli are inaudible to that ear. The upper age limit on participants will be 80 years of age, to avoid the rising prevalence of dementia at older ages (Piccirillo et al. 2008) while still including a wide age range. We will attempt to recruit equal numbers of men and women, although we will prioritize including all interested participants over achieving parity. All statistical analyses will be conducted with sex as an additional predictor, although we do not expect sex to affect experimental outcomes.

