### Primary Outcome: Speech recognition in two-talker masking speech

Perceptually Robust English Sentence Test Open-set (PRESTO) sentences (Tamati, Gilbert, and Pisoni 2013) will be presented in quiet and with a two-talker masker at an average target-to-masker ratio of +5 dB. Participants will hear lists 7 and 15 in quiet and 13 and 17 in noise, to limit the impact of cross-list differences in difficulty (Faulkner et al. 2015) on speech recognition accuracy. Performance will be quantified as the percentage of keywords correctly identified across sentences (152 keywords per condition).

For the two-talker masker, PRESTO sentences from unused sentence lists will be concatenated into a running speech stream. Two samples of this running stream will be sampled and superimposed to form the competing speech for each target sentence. Two talkers will be used to maximize the impact of informational masking on speech recognition (Freyman, Balakrishnan, and Helfer 2004). The masking speech will start 0.5 s prior to the target speech and stop 0.5 s after to ensure that participants are given a timing cue to distinguish the masker from the target. The combination of target sentence and maskers will be fixed (“frozen”) across participants to account for fluctuations in the amount of energetic masking that arise from interactions between targets and maskers (Buss et al. 2020). We will fix long-term target-to-masker ratio because that is conventional in speech recognition research. In addition, we will calculate short-term envelope ratio, defined as the proportion of time in which the target speech has a larger instantaneous envelope than the masker for each sentence.

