### Step 2: Predict speech recognition accuracy in quiet

We expect both modulation detection thresholds to be significant predictors of sentence recognition accuracy, which will account for approximately half of the variance. We will compare the likelihood of generalized linear regression models which include only modulation detection thresholds against models which also include the memory components identified in step 1 to determine if these memory components are significant predictors of speech recognition in quiet. We will verify that modulation detection thresholds and working memory task performance are not correlated, as we found in participants with cochlear implants ( $r = -0.36$ ,  $r = -0.15$  for spectral and temporal threshold correlations with digit span,  $p > 0.10$ ).

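### SAP Step 3 can stop the planned mediator analysis on a fit comparison that has no metric, margin or interval

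*SAP*

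**What the plan says.** SAP Step 2 builds a model for sentence recognition in quiet from two modulation thresholds, "which will account for approximately half of the variance", and uses a likelihood comparison to decide whether memory components add to it.

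Step 3 then says: "We will extrapolate the predictor model for speech recognition in quiet developed in step 2 to the case of speech recognition in competing speech". Two outcomes follow.

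- Stop: "If the model performs as well for speech in speech as it does for speech in quiet, we would infer that two-talker speech maskers do". The rest of that sentence is negative: it denies that the masker adds variability that matters, and closes with the words "introduce meaningful variability into speech recognition outcomes and stop here".
- Continue: "If the speech in quiet model is a worse fit, we will add stream segregation to the predictor model". Stream segregation must then predict unique variance, and the thresholds and memory factors are tested as predictors of segregation.

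Neither document gives a fit measure, a margin, a test or an interval for this comparison, or says what is held fixed when the quiet model is extrapolated. The likelihood comparison in Step 2 does not fill the gap, because it compares models within quiet only.

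The Protocol's Sample Size and Power Analysis section commits to running the mediator analysis despite limited power, and makes estimating its effect sizes the goal of the pilot. The sample is fixed under Participants: "30 participants who lost their hearing and received cochlear implants as adults will participate in this study". The primary outcome is percent correct with "152 keywords per condition".

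**The concern.** Step 3 draws a scientific conclusion (the masker adds no meaningful variability between listeners) and a stop decision from the difference between two fit statistics in 30 people. With no allowance for sampling error, either outcome can arise by chance. The answer also depends on choices the SAP leaves open: the fit measure and how much of the quiet model is carried over.

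The two errors are not equally costly. A false stop removes the stream-segregation and mediator analyses, which the Protocol treats as the purpose of the pilot. A false report of worse fit only misstates whether the masker added variability, because segregation must still pass its own test.

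**Working it through.** **The plan's own figure.** The Protocol states 29 participants for r = 0.5. Fisher z, two-sided 0.05, power 0.80: ((1.960 + 0.842)/0.5493)² + 3 = 29.01, so 29 reproduces. That figure concerns a correlation. The documents give no error rate for the Step 3 rule.

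**Inputs from the documents.** N = 30; 152 keywords per condition; R² in quiet about 0.5 (SAP Step 2) or 0.64 (preliminary data, Protocol Predictor 1); predictors are two thresholds, one or more memory components, and sex.

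**Assumed, because the documents are silent.** Mean scores; a mean masker drop of 0 to 2 logits; between-listener SD of 0.7 to 1.0 logit; correlation of 0 to 1 between a listener's residuals in the two conditions.

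**Model.** Logit accuracy in quiet = m + L + e. In competing speech it is m − d + L + e′ + u, where L is the predictor part, d a uniform drop and u the masker-added listener effect with SD τ. Keyword counts are binomial. The rule is read as: stop if R²(quiet) − R²(competing) ≤ 0.

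**1. Refitted model, R² on proportion correct.** Quiet R² is 0.5, means are ±0.6 logit, with 4 predictors and 4,000 replicates per setting. With total logit variance 1, nominal R² in competing speech is 0.5/(1 + τ²).

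| τ (logit) | Nominal R² | Stops, residual correlation 1 / 0.7 / 0 |
|---|---|---|
| 0 | 0.50 | 50.7% / 51.0% / 49.5% |
| 0.3 | 0.459 | 35.4% / 39.0% / 42.5% |
| 0.5 | 0.40 | 20.8% / 26.4% / 33.0% |
| 0.7 | 0.336 | 11.9% / 16.3% / 21.4% |

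At τ = 0 the SD of the R² difference is 0.066, 0.111 or 0.157. The nominal loss at τ = 0.5 (0.50 − 0.40 = 0.10) is therefore only about 1.5, 0.9 or 0.6 of these SDs. Other assumed means, with quiet R² about 0.58, gave false stops of 24 to 33% at τ = 0.4 and 11 to 16% at τ = 0.7. On logit scores the figure at τ = 0.4 was 20 to 24%.

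**2. Worse fit reported when τ = 0.**

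| Reading of the extrapolation | Rate of worse fit |
|---|---|
| Refitted, means symmetric about 50% or no drop | 49 to 51% |
| Refitted, R² on logit scores | 44 to 50% |
| Refitted, asymmetric means, raw-score R² | 32 to 42% |
| Refitted, asymmetric means, proportion of deviance explained | 48 to 53% |
| Refitted, asymmetric means, raw RMSE or deviance | 75 to 98% |
| Intercept only re-estimated, scale-free measures | 51 to 77% |
| All coefficients frozen, drop of 1 point | 59 to 60% |
| All coefficients frozen, drop of 2 points | 66 to 70% |
| All coefficients frozen, drop of 4 points | 83 to 86% |
| All coefficients frozen, drop of 6 points | 96 to 97% |
| All coefficients frozen, drop of 10 points or more | 100% |

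The top of the intercept-only range (about 76 to 77%) comes from settings with residual correlation 0. There, residual variance is equal in the two conditions but listeners change rank. That is null for a fit comparison, but not strictly null for listener-by-condition variance.

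**3. Would a margin on R² be enough?** Holding false worse fit to 5% needs a margin of about 0.11, 0.18 or 0.26 (residual correlation 1, 0.7, 0). A real τ = 0.5 is then detected in only 40%, 22% or 13% of studies. At N = 30 the R² difference carries too little information.

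**4. Direct estimate.** Compare the between-participant variance of the competing-minus-quiet logit difference with the error estimated from the two lists per condition. A test of this kind fired in about 6 to 9% of studies at τ = 0 and 84 to 96% at τ = 0.4 with binomial error. With extra list-level error (beta-binomial, ρ = 0.01) it fired in 61 to 74% at τ = 0.4. It is slightly liberal, but separates the two cases far better.

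**The case against.** Several points on the other side are sound.

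- **The rule is not blind.** In one set of runs the refitted comparison reported worse fit in 47 to 52% of studies at τ = 0, 67 to 76% at 0.4 and 84 to 89% at 0.7. A reader might infer that it cannot discriminate at all; these figures do not support that. Lost fit does partly reflect unexplained variance between listeners.
- **Near-certain worse fit is conditional.** A reader might infer that worse fit is practically guaranteed. That needs every quiet coefficient frozen, intercept included, and a mean drop of about 6 to 10 points or more. The documents state neither, and freezing the intercept is the least natural choice when a masker is expected to lower scores.
- **No single error rate belongs to the plan.** The SAP names no metric, and its reference to meaningful variability suggests some judgement of size. A strict inequality is an assumed reading.
- **A false worse fit declares no mediation.** It leads to the analysis the Protocol already promises.
- **This is a pilot.** Non-significant mediator results are to be read in the light of power.

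These limit the claim but do not remove it. Judgement of size without a stated size leaves the stop decision open until the data are seen. An estimation goal also argues against a gate that can prevent the estimate.

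**Conclusion.** The Step 3 rule is wrong as written and should be changed before analysis. It responds to masker-added variability, but it is uncalibrated and can stop the study short of its stated goal.

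On a refitted model and a scale-free measure, it stops wrongly in about 20 to 33% of studies when the masker adds an SD of 0.4 to 0.5 logit. It reports worse fit in about 45 to 50% when the masker adds none; across metrics that figure runs from 32 to 98%. The sizes rest on assumed mean scores, listener SDs and residual correlations, and on reading the comparison without a margin. The absence of a metric, margin, interval and refitting rule rests on the text alone. So does the conflict between the stop and the Protocol's commitment to the mediator analysis.

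**What to change.** In SAP Step 3:

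1. Remove the stop. Run the stream-segregation and mediator analyses whatever the fit comparison shows, in line with the Protocol's sample-size section.
2. Estimate masker-added variability directly. Fit a binomial mixed model with a participant-by-condition variance, or compare the between-participant variance of the competing-minus-quiet logit difference with within-participant error from the paired lists (7 and 15 in quiet, 13 and 17 in noise).
3. Report that SD with a 95% interval. Conclude no meaningful variability only if the upper limit lies below a margin the sponsor fixes before analysis; otherwise report the result as inconclusive. Neither result affects whether the mediator analysis is run.
4. If the fit comparison is kept as description, refit intercept and slopes in competing speech and give a paired bootstrap interval for the difference in R².

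The cost is SAP wording and one extra model, with no new data. The interval may be wide with 30 participants. In simulation with no added variability, the upper limit fell below 0.3 logit in 29 to 76% of studies and below 0.4 logit in 63 to 98%, depending on assumed list-level error and shift. Those two values only illustrate; they are not proposed margins.

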This proposal extends the use of auditory and cognitive predictors to examining individual differences in the ability to track and understand a target speaker in competing noise. In addition to the direct effects of auditory resolution and working memory on recognition of target speech, we propose that auditory resolution and cognitive factors also indirectly affect speech recognition in competing speech by determining the listener’s ability to segregate target speech from competing sound sources. Competing speech can act in two ways: it can overlap with target speech and mask portions of the target which provide speech information (“energetic” masking), and it can intrude on the listener’s processing of the target speech information (“informational” masking) (Kidd et al. 2008; Shinn-Cunningham and Best 2008). Individuals with normal hearing can rely on auditory cues, such as voice pitch, to help separate target and masking speech from one another, but individuals with cochlear implants have difficulty hearing voice pitch differences (Chatterjee and Peng 2008; Deroche et al. 2014) and need large differences between target and masker voices to recognize speech in noise (Meister et al. 2020).

Hypothesis: Stream segregation mediates the relationship between speech recognition in competing speech, auditory resolution and working memory

The premise of this proposal is that individual differences in auditory resolution and cognition affect speech recognition in competing speech directly by affecting recognition of target speech and indirectly by affecting the difficulty of segregating target speech from competing speech. These direct and indirect pathways can be quantified

in a partial mediator model (Baron and Kenny 1986), with stream segregation as the variable that mediates the predictive power of auditory resolution and cognition for speech recognition in competing speech. In this project, we will test whether a partial mediator model describes the relationship between speech recognition in competing speech, stream segregation, and auditory resolution and cognition.

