## Design

### Sample Size and Power Analysis

Our preliminary data described below indicate that the measures of auditory resolution and working memory we use will correlate with sentence recognition accuracy with coefficients of at least  $r = 0.5$ . Replicating correlations of this magnitude in the proposed study with  $\alpha = 0.05$  and  $\beta = 0.80$  would require 29 participants. We do not currently have an estimate of the indirect path effect sizes in the mediator model because the stream segregation task we are proposing is novel. For a mediator analysis, the needed sample size to achieve  $\beta = 0.80$  is at least 34 participants if the relationship between auditory resolution, working memory and stream segregation and the relationship between stream segregation and speech recognition in noise have effect sizes of 0.59 (Fritz and MacKinnon 2010). Larger sample sizes would be needed for smaller effect sizes. The limited timeline for this project makes it infeasible to power the study for smaller indirect path sizes (e.g. 71 participants if both effect sizes are 0.39), so the goal of this pilot project will be to provide an estimate of the magnitude of these effect sizes as a basis for determining feasibility of subsequent work. The mediator analysis will still be conducted, but interpretation of non-significant outcomes will be framed within the statistical power of the available sample.

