#### Predictor 1: Auditory resolution

Preliminary data from 20 participants with cochlear implants tested in the lab indicates that spectral and temporal modulation detection thresholds predict PRESTO sentence recognition accuracy in quiet. In a generalized linear regression model, spectral and temporal modulation detection thresholds accounted for  $R^2 = 0.64$  of the variance in recognition accuracy (spectral  $\beta = -0.76$ , temporal  $\beta = -0.47$ ). We will repeat these tasks in this study.

Modulation detection thresholds will be measured with a three-interval, three-alternative forced-choice task. The carrier signal is a 60 dB SPL, 400 ms long noise burst with energy between 350 and 6500 Hz (selected to match the stimuli in Litvak et al. 2007), gated on and off with 20 ms  $\sin^2$  ramps. Carriers are modulated in the target interval and was unmodulated in the other two intervals. Feedback is given after each trial. In the temporal modulation detection task, the target interval is sinusoidally amplitude-modulated at a 100 Hz rate, which has been previously shown to correlate with speech recognition in listeners with cochlear implants when presented via direct stimulation (Fu 2002; Luo et al. 2008) and via a loudspeaker (Won et al. 2011). In the spectral modulation detection task, the target interval is spectrally modulated at 0.5 ripples per octave, which has been previously shown to correlate with speech recognition when presented via a loudspeaker (Anderson et al. 2012; Litvak et al. 2007; Saoji et al. 2009). Carrier level for every interval is randomly varied between -3 and +3 dB Sound Pressure Level (SPL) to diminish the availability of loudness differences between modulated and unmodulated intervals (McKay and Henshall 2010).

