## **Statistical Analysis Plan**

Data analysis will proceed in stages to confirm that our results replicate previous findings with at-home testing and to ensure the assumptions necessary to test for a mediating relationship are met.

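### SAP Step 3 can stop before stream segregation is analysed, on an equal-fit result that does not rule out mediation

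*SAP*

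**What the plan says.** The Protocol's Objectives set out one labelled hypothesis, a partial mediator model "with stream segregation as the variable that mediates the predictive power of auditory resolution and cognition for speech recognition in competing speech". Its Sample Size and Power Analysis section says that "the goal of this pilot project will be to provide an estimate of the magnitude of these effect sizes", meaning the indirect-path sizes, and adds: "The mediator analysis will still be conducted, but interpretation of non-significant outcomes will be framed within the statistical power of the available sample". Neither statement depends on how well any model fits.

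The SAP introduction says the staged analysis serves to confirm earlier findings under at-home testing and "to ensure the assumptions necessary to test for a mediating relationship are met". Step 3 then carries the quiet model over to competing speech. If it performs equally well, "we would infer that two-talker speech maskers do not introduce meaningful variability into speech recognition outcomes and stop here". The only route to the mediator is the other branch: "If the speech in quiet model is a worse fit, we will add stream segregation to the predictor model". The regression of segregation on thresholds and memory comes last, after that branch.

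The SAP names no fit statistic, margin or test for equal or worse performance. It does not say whether the quiet coefficients are carried over or refitted.

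**The concern.** The gate does not address mediation. A model containing thresholds and memory but not segregation captures their total effect on competing-speech accuracy, direct and indirect together. Good prediction by that model shows the effect that the hypothesis proposes to split; it is not evidence that there is nothing to split. The inference about the masker fails too, because R² can be the same in both conditions while segregation explains much of what the predictors leave over.

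A worse fit in competing speech than in quiet is not an assumption of a mediation test, so the gate does not serve the purpose given in the SAP introduction. If it closes, the hypothesis goes untested and the planned analysis yields none of the path estimates the pilot exists to provide. The segregation data would still be collected, so the estimates could be recovered, but only post hoc and outside the SAP.

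**Working it through.** **Inputs from the documents.** n = 30 (Protocol, Participants). Indirect paths of 0.59 or 0.39 (Sample Size and Power Analysis). Quiet R² of about one half (SAP Step 2: "which will account for approximately half of the variance"), or 0.64 in the preliminary data (Predictor 1: Auditory resolution).

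**Assumed.** The path sizes are standardised coefficients. The direct effect c', the competing-speech R², the quiet–noise residual correlation, the mean drop, any tolerance and the full-mediation pair (0.85, 0.83) are not in the documents.

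**The plan's own figures.** For r = 0.5, two-sided α = 0.05 and 80% power: n = ((1.960 + 0.842)/atanh 0.5)² + 3 = (2.802/0.549)² + 3 ≈ 29.0, matching the stated 29. The mediation sizes are also consistent with about 80% power. By simulation with no direct path and unit-variance errors, n = 34 at 0.59 gives 0.83 (bias-corrected bootstrap) or 0.77 (both paths significant); n = 71 at 0.39 gives 0.82 or 0.78.

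**Does equal fit exclude mediation?** Let a be predictor to segregation, b segregation to competing-speech accuracy, and c' the direct effect. Then:

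- R² without segregation = (c' + ab)²
- unique variance of segregation = b²(1 − a²)

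| a, b | c' | ab | R² without segregation | Unique part | R² with segregation |
|---|---|---|---|---|---|
| 0.59, 0.59 | 0.36 | 0.348 | 0.708² = 0.501 | 0.348 × 0.652 = 0.227 | 0.728 |
| 0.59, 0.59 | 0.452 | 0.348 | 0.800² = 0.640 | 0.227 | 0.867 |
| 0.39, 0.39 | 0.555 | 0.152 | 0.707² = 0.500 | 0.152 × 0.848 = 0.129 | 0.629 |
| 0.85, 0.83 | 0 | 0.706 | 0.498 | 0.689 × 0.278 = 0.191 | 0.689 |

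In the first row the predictors fit competing speech as well as the SAP expects them to fit quiet. Yet 0.348/0.708 = 49% of the effect is indirect, and segregation explains 0.227/0.499, about 45%, of what is left. The last row shows the same under full mediation.

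**How often would the rule fire when mediation is real?** Simulation at n = 30: 20,000 replicates per cell, three independent predictors, residual correlation 0.3 and 0.6. Unless noted, the analysis stops if R² in noise is at least R² in quiet.

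| Reading of equal fit | True R², quiet / noise | Stops |
|---|---|---|
| Full quiet equation carried over, no mean drop | 0.50 / 0.50 | 27–34% |
| Same, 0.25 SD drop | 0.50 / 0.50 | about 17% |
| Same, 0.5 SD drop | 0.50 / 0.50 | 2–4% |
| Same, 1 SD drop | 0.50 / 0.50 | 0% |
| Slopes only carried over | 0.50 / 0.50 | 33–38% |
| Refitted | 0.50 / 0.50 | 49–51% |
| Refitted | 0.50 / 0.39 | 20–25% |
| Refitted | 0.64 / 0.50 | 10–16% |
| Refitted, a = b = 0.59, c' = 0 | 0.50 / 0.12 | 1–2% |
| Refitted, up to 0.10 lower allowed | 0.50 / 0.50 | 76–83% |
| Refitted, up to 0.10 lower allowed | 0.64 / 0.50 | 39–42% |

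With one composite predictor and equal fit read as not significantly worse, it stops in about 97.5% of studies at 0.50 / 0.50 and about 90% at 0.50 / 0.40. Part of the spread is noise: at n = 30 the sampling SD of R² is about 0.125 at a true value of 0.50 and 0.104 at 0.64.

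**What a stop would lose.** In the a = b = 0.59, c' = 0.36 case, both paths are significant in 84% of studies with three predictors, 79% with four, 72% with five and about 94% with one composite. At a = b = 0.39 and R² 0.50 the figure is about 30% with three predictors and 48% with one composite.

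**The case against.** The wording of Step 3 points to applying the quiet model itself rather than refitting it, and the Protocol says implant users struggle in competing sound. If the whole equation, intercept included, is carried over and scores fall by 0.5 SD or more, the rule fires in at most 4% of the simulated studies. The higher rates need refitting or a tolerance that the documents do not give, and the direct effects were chosen to produce equal R².

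The simulations also use normal-theory R², not the planned generalized linear models of a keyword percentage. They leave out sex and a possible second memory component; with five predictors, full carry-over and no drop, stopping is 18–24%. The Protocol's assurance that the mediator analysis will go ahead answers the preceding remark on power, not this gate. Finally, this is a 30-person pilot whose segregation data are kept either way.

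Much of this stands as to likelihood: no single stopping rate can be defended, and the stated estimation goal is better evidence of conflict than the assurance. It does not rescue the inference. If the gate opens because average scores fell, it opened for a reason unrelated to individual differences or mediation. Under refitting, a mean drop has no effect on it. The algebra needs only a linear model.

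**Conclusion.** The stop rule is wrong as written. Equal fit in quiet and in competing speech does not exclude mediation and does not show that the masker adds no meaningful variability. At the Protocol's path size of 0.59, with an assumed direct effect of 0.36, segregation would add 0.23 to an R² of 0.50 and never be examined.

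The stop is conditional, so the hypothesis can, but need not, go untested. The chance ranges from 0% to about 97.5% across the readings tried, and the documents do not allow it to be narrowed. The algebraic result rests on a linear model with standardised paths. The rates rest in addition on the assumptions listed with the calculations.

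**What to change.** Delete the stop rule in SAP Step 3. In all participants, whatever the Step 2 result, fit:

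1. segregation on the modulation thresholds, the retained memory components and sex (the Protocol's Participants section puts sex in every analysis);
2. competing-speech accuracy on the same predictors plus segregation.

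Report a, b and c'. Keep the quiet-versus-competing-speech comparison as descriptive, naming the fit measure and stating whether coefficients are carried over or refitted. Reconcile Step 3 with the SAP introduction and with the Protocol's Sample Size and Power Analysis section.

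As an optional addition that serves the estimation goal, report the indirect effect ab with a bootstrap 95% interval. At n = 30 and a = b = 0.59 (ab = 0.35), the median interval runs from about 0.13 to 0.58, with 94% coverage (1,500 simulated datasets, 1,000 resamples each, one composite predictor).

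The cost is SAP wording and two regressions on data already planned, plus one bootstrap if wanted.

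### Step 3 tests segregation for unique variance without adjusting for each participant's own quiet PRESTO score, which may cost precision or may credit general recognition ability to segregation

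*SAP*

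**What the plan says.** Under Primary Outcome, the Protocol gives every participant the same sentence test twice: PRESTO sentences "will be presented in quiet and with a two-talker masker at an average target-to-masker ratio of +5 dB". Lists 7 and 15 are heard in quiet, lists 13 and 17 in noise. Each condition is scored as percent correct of 152 keywords.

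In SAP Step 2 the quiet score is an outcome. It is modelled from the two modulation thresholds, with and without the memory components kept in Step 1. The thresholds are expected to be significant predictors, "which will account for approximately half of the variance". The Protocol's Participants section adds sex to every analysis.

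SAP Step 3 carries those predictors over to accuracy in competing speech. If the fit is worse than in quiet, "we will add stream segregation to the predictor model and test whether it predicts unique variance in speech recognition accuracy in competing speech". A positive result is to be read as showing that segregation is a separate component of recognising speech among competitors.

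Neither document enters the individual quiet score as a covariate for the masked score, or analyses a masked-minus-quiet difference.

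**The concern.** Step 3 uses the predictors of quiet recognition but not quiet recognition itself. If thresholds explain about half of the quiet variance, much of what remains may be person-level recognition ability that also helps in competing speech. In the planned model that ability sits in the error term. Two consequences are possible.

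- **Precision.** If the leftover ability is unrelated to segregation, it is noise that a score already collected could remove. This matters in a study of 30 people whose stated aim is to estimate path sizes.
- **Attribution.** If the leftover ability is related to segregation, the segregation coefficient absorbs part of it. The test for unique variance could then be positive because good recognisers do well on both tasks, and the conclusion that segregation is something separate would not follow.

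**Working it through.** **The plan's own figure.** The Protocol says that detecting r = 0.5 "would require 29 participants", at α = 0.05 and 80% power. By Fisher's z, two-sided: n = ((1.960 + 0.842) / atanh 0.5)² + 3 = (2.802 / 0.5493)² + 3 = 29.01. The figure reproduces, but it concerns a simple correlation. No power is stated for the Step 3 segregation test. The mediator sample sizes (34 if the two relationships "have effect sizes of 0.59"; "71 participants if both effect sizes are 0.39") come from a cited source and were not re-derived.

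**Inputs from the documents.** N = 30; two thresholds; one or two memory components (the two structures that Step 1 names); sex; 152 keywords per condition. Binomial error at 50% correct is √(0.25/152) = 4.1 points, so keyword sampling is a modest source of noise in the quiet score.

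**Inputs assumed.** After removing thresholds, memory and sex, write Q for the quiet score and S for segregation, both standardised, with correlation c. Take masked score = bS + ρQ + √(1 − ρ²)e, so that b is in residual SD units. The documents give neither ρ nor c. The test is the OLS t-test of S with and without Q, by simulation, with one memory component.

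**Case 1: c = 0, b = 0.5.** The partial correlation is 0.5/√1.25 = 0.45, between the plan's 0.39 and 0.59. Power without the quiet score is about 66%.

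| ρ | 0 | 0.3 | 0.5 | 0.6 | 0.7 |
|---|---|---|---|---|---|
| Power with the quiet score | 65% | 68% | 76% | 81% | 88% |

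Repeat runs agree within about two points. The standard error scales with √(1 − ρ²): from about 0.20 to 0.20 × 0.866 ≈ 0.18 at ρ = 0.5, and to 0.20 × 0.714 ≈ 0.15 at ρ = 0.7, allowing for rounding and one lost degree of freedom.

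At the plan's own path sizes, read as partial correlations, with two memory components and ρ now taken as the correlation of Q with the whole residual masked score:

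- At 0.39, power is about 0.50 without the score. With it, power is 0.49, 0.51, 0.56, 0.70 and 0.95 at ρ = 0, 0.2, 0.4, 0.6 and 0.8.
- At 0.59, power is already about 0.90. With the score it is 0.95 at ρ = 0.4 and 0.995 at ρ = 0.6.

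If the predictors explain half of both scores with equal coefficients, the raw quiet-masked correlation is 0.5 + 0.5ρ. Then ρ = 0.4, 0.6 and 0.8 mean raw correlations of 0.7, 0.8 and 0.9.

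**Case 2: c > 0, no true effect (b = 0).** The planned coefficient is biased by ρc.

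| ρ | c | Bias ρc | Rejects, planned | Rejects, with quiet score |
|---|---|---|---|---|
| 0.5 | 0.3 | 0.15 | 11% | about 5% |
| 0.3 | 0.5 | 0.15 | 12% | about 5% |
| 0.6 | 0.3 | 0.18 | 14% | about 5% |
| 0.6 | 0.5 | 0.30 | 30% to 33% | about 5% |

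A hand check with standard error 0.20: bias 0.15 is 0.75 standard errors, and Φ(−1.21) + Φ(−2.71) = 0.113 + 0.003 ≈ 12%. If both correlations are only 0.3, the bias is 0.09, or 0.45 standard errors, and Φ(−1.51) + Φ(−2.41) = 0.066 + 0.008 ≈ 7%.

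**Case 3: c > 0, true effect b = 0.5.**

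- At ρ = 0.5, c = 0.3 the planned model rejects 85% of the time against 71% with the score. Its mean estimate is 0.50 + 0.15 = 0.65.
- At ρ = 0.3, c = 0.5 the figures are 86% against 57%, again with a planned estimate of 0.65. The standard error rises from 0.20 to 0.23, since √((1 − 0.09)/(1 − 0.25)) = 1.10.

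The planned model's higher rejection rate here comes partly from upward bias.

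**Limits.** A linear model stands in for the generalized linear model. Ceiling and floor effects, measurement error in the quiet score and the Step 3 stopping rule are not modelled.

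**The case against.** The planned model follows the stated hypothesis. The Protocol's Objectives specify a partial mediator model with direct paths from resolution and memory, and target recognition lies on those paths. Adjusting for the quiet score removes part of the effects that the model is meant to estimate. This stands, and it is why the remedy is an added model and not a replacement.

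Limited power is already disclosed: the Protocol calls the study a pilot to estimate effect sizes and will read non-significant results in the light of the power available. That stands too, but it does not address attribution.

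The segregation metric is a difference from a baseline condition and uses digits, chosen because they are easy to identify. This may reduce its overlap with quiet recognition but does not rule it out.

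A reader might infer that the planned test has much less power than the same 30 people ("30 participants who lost their hearing and received cochlear implants as adults will participate in this study") could give. The documents do not support this. They report no quiet-masked correlation, the gain is about 2 points at 0.3, and there is a small loss at 0. A reader might also take the quiet score to be the best covariate available, or its inclusion to be free. No figure supports the first: binomial error is one noise source, list differences and home set-up are others, and no retest reliability is given. Case 3 contradicts the second.

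**Conclusion.** The omission is real and is visible in the documents. Its size is not, because it depends on two undocumented correlations.

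- If segregation is unrelated to the quiet score given the covariates, adding the score changes power from about 66% to between 65% and 88% for residual quiet-masked correlations of 0 to 0.7. A gain of about 10 points needs a correlation near 0.5.
- If the two overlap, the issue is bias rather than power. With no true effect, the planned test rejects about 11% to 33% of the time in the four scenarios tabulated, about 7% when both correlations are 0.3, and about 5% in every case with the score.

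Either way, the planned model alone does not secure the conclusion that segregation is a separate component, because it cannot distinguish segregation from unmeasured general recognition ability. This does not make the planned model wrong for the direct paths of thresholds and memory.

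**What to change.** In SAP Step 3, pre-specify one added model for competing-speech accuracy containing the thresholds, the memory components, sex, segregation and the participant's quiet PRESTO score (lists 7 and 15). State that the conclusion about segregation as a distinct component rests on its coefficient and interval in this model. Keep the planned model without the quiet score for the direct paths of thresholds and memory, and report both segregation estimates side by side. Report also the residual quiet-masked and segregation-quiet correlations, which later work will need for planning.

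The cost is SAP wording, one further model and one degree of freedom, with no new data or participants. The interval for segregation can widen if segregation and the quiet score are strongly correlated while the residual quiet-masked correlation is low (standard error 0.20 to 0.23 at correlations of 0.5 and 0.3).
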